## **4 Change to protocol specified analyses**

Not applicable

## **5 Appendix**

### **5.1 Imputation rules**

#### **5.1.1 Study drug**

Not applicable

#### **5.1.2 AE date imputation**

AE date imputation is based only on a comparison of the partial AE start date to the treatment start date as mentioned in the Table 1-2 below.

1. If the AE start date year value is missing, the date uncertainty is too high to impute a rational date. Therefore, if the AE year value is missing, the imputed AE start date is set to NULL.
2. If the AE start date year value is less than the treatment start date year value, the AE started before treatment. Therefore:
  - a. If the AE year is less than the treatment year and the AE month is missing, the imputed AE start date is set to the mid-year point (01JulYYYY).

- b. Else if the AE year is less than the treatment year and the AE month is not missing, the imputed AE start date is set to the mid-month point (15MONYYYY).

3. If the AE start date year value is greater than the treatment start date year value, the AE started after treatment. Therefore:

- a. If the AE year is greater than the treatment year and the AE month is missing, the imputed AE start date is set to the year start point (01JanYYYY).
- b. Else if the AE year is greater than the treatment year and the AE month is not missing, the imputed AE start date is set to the month start point (01MONYYYY).

4. If the AE start date year value is equal to the treatment start date year value:

- a. And the AE month is missing or the AE month is equal to the treatment start month, the imputed AE start date is set to one day after treatment start.
- b. Else if the AE month is less than the treatment start month, the imputed AE start date is set to the mid-month point (15MONYYYY).
- c. Else if the AE month is greater than the treatment start month, the imputed AE start date is set to the start month point (01MONYYYY).

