**Figure 1: Study design****Planned number of patients and randomization**

At Baseline approximately 200 patients will be randomized. Randomization will occur to one of the following two treatment groups in a ratio of 1:1.

- Group 1 (secukinumab): secukinumab as 1 (1.0 mL pre-filled syringe (PFS) of 150 mg dose) s.c. or 2 (2 x 1.0 mL PFS of 150 mg dose, 300 mg) s.c. injections according to axSpA or PsA disease at Baseline, Weeks 1, 2, and 3, followed by administration every 4 weeks starting at Week 4.
- Group 2 (placebo): placebo as 1 (1.0 mL PFS) or 2 (2 x 1.0 mL PFS) s.c. injections according to axSpA or PsA disease at Baseline, Weeks 1, 2, 3, followed by administration every 4 weeks starting at Week 4.

Patients will receive study treatment at Baseline, Weeks 1, 2, and 3, followed by treatment every 4 weeks through Week 52 (last dose given at Week 48). At Week 24, patients originally randomized to placebo will switch to receive secukinumab 150 mg (1 injection of secukinumab 1 mL/150 mg) or secukinumab 300 mg (2 injections of secukinumab 1 mL/150 mg) in open-label fashion without a loading regimen.

Blinding to the original treatment assignment will be maintained until after the Week 52 database lock and analyses are completed. However, original randomized treatment assignment to secukinumab or placebo will remain double-blinded to all patients, investigators, and site personnel, whereas the Sponsor (including the Region Europe Clinical Team, statisticians and data management) will be unblinded after the Week 24 database lock (protocol [Section 3.5](#)) and analyses are completed (protocol [Section 9.7](#)).

Patients will be stratified at randomization on the basis of PsA or axSpA disease.

Based on enrollment target, it is planned that approximately 50% of randomized patients should be PsA and approximately 50% axSpA patients to ensure a balanced patient population for the assessment of efficacy and safety.

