#### 2.1.1 General definitions

**Study treatment:** Study treatment refers to:

Secukinumab 150 mg provided in 1 ml PFS or Secukinumab placebo provided in 1 ml PFS.

**Study treatment start and end date:** Study treatment start date is defined as the first date when a non-zero dose of study drug is administered and recorded on the Drug Administration Record (DAR) CRF page. Similarly, study drug end date is defined as the last date when a non-zero dose of study drug is administered and recorded on the DAR CRF page of the core study.

**Study day:** Study day will be calculated as (event date – study drug start date + 1 day) for events that occurred on or after study drug start date (e.g.visit, lab samples, AEs). For events prior to study drug start date (e.g., time of diagnosis), study day will be negative and calculated as (event date – study drug start date). Note that study drug start date is study day 1 and the day before study drug start date is study day -1 (i.e. no study day 0).

Due to the study drug dosing schedule, one month will be considered as 28 days. However, for “time since event” data (e.g., medical history), one month will be considered as 365.25/12 days for events that occurred prior to study Day 1. Time from events prior to the start of study drug, e.g., time since diagnosis, is calculated as the difference between the start date of study drug and the date of prior event.

Note that, the first dose day is Day 1, and the day before the first dose day is counted as Day -1 (not Day 0).

**Baseline and post baseline:** In general, a *baseline* value refers to the last measurement made prior to administration of the first dose of study treatment. A post-baseline value refers to a measurement taken after the first dose of study treatment.

**Treatment Period:** There are two treatment periods for this study defined as :

Treatment Period 1 is defined as a 24 Week placebo-controlled, double-blind treatment period starting from baseline till Week 24.

Treatment Period 2 is a 28 Week open-label treatment period starting from Week 28 (end of Week 24) till Week 52.

**Lost to follow up:** The patients whose study completion status is unclear because they fail to appear for study visits without stating an intention to withdraw.

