### **2.8 Safety analyses**

For all safety analyses, the Safety set will be used.

Summaries will be performed separately for first (Week 1-24) and entire treatment periods. Use of data up to and including the last visit before rescue provides and unbiased comparison between secukinumab and placebo; data collected beyond week 24 are included in analyses which summarize the entire treatment period.

Safety analyses will be performed by PsA and AxSpA patients on treatment received or actual treatment as described below:

The actual treatment or treatment received for summaries of safety data will differ to the treatment assigned at randomization only if a subject received the wrong treatment during the entire study.

For those patients who received not the treatment randomized, i.e. who received erroneously the wrong treatment at least once, an additional AE listing will be prepared displaying which events occurred after the treatment errors.

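### Partial AE start dates are imputed against the first dose only, so events that ended before dosing can count as treatment-emergent and some post-switch events can fall into Week 1-24

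*SAP*

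**What the plan says.** **The rule.** SAP 5.1.2 states that "AE date imputation is based only on a comparison of the partial AE start date to the treatment start date". Four of its branches matter here:

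- Same year as the first dose, with the month missing or equal to the first-dose month: "the imputed AE start date is set to one day after treatment start" (rule 4a).
- Same year, with a known month after the first-dose month: the first of that month (rule 4c).
- Later year, month known: the first of that month (rule 3b).
- Later year, month missing: 1 January of that year (rule 3a).

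No cell or legend entry in SAP Table 5.1-2 uses the Week 24 switch date or the AE end date. The table itself labels the rule 4a cells as uncertain.

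**The reference date.** Under SAP 2.1.1, "Study treatment start date is defined as the first date when a non-zero dose of study drug is administered". The same section counts the placebo syringe as study treatment, so in the placebo arm the reference is the first placebo injection.

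**Where the dates are used.**

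- SAP 1.1: "At Week 24, patients originally randomized to placebo will switch to receive secukinumab 150 mg" (or 300 mg).
- SAP 2.1.1: "Treatment Period 1 is defined as a 24 Week placebo-controlled, double-blind treatment period starting from baseline till Week 24".
- SAP 2.8: "Summaries will be performed separately for first (Week 1-24) and entire treatment periods".
- SAP 2.4.1 stops exposure at the switch.
- SAP 2.8.1 makes an event treatment-emergent if it starts after the first dose, or was present before it and worsened. There is no condition on the end date.

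Protocol 6.1 records AEs from consent in randomized patients, and protocol 7.1 collects both start and end dates.

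**The concern.** A first-dose anchor answers one question: did the event start before or after dosing began? Here it falls short in two ways.

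First, rule 4a can date an event after its own recorded end. That date is impossible, and it turns a resolved screening event into a treatment-emergent one although the end date that would prevent this is in the database.

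Second, the trial has a second boundary at Week 24, where the controlled period ends and placebo patients change drug. The rule cannot see that boundary. When an event is dated too early across it, the Week 1-24 numerator gains an event while the exposure denominator still stops at the switch. Week 1-24 is the only placebo-controlled safety comparison in the trial.

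**Working it through.** The plan gives no figure on this point to reproduce, so the check applies the rule in SAP 5.1.2 directly.

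**Inputs**

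- Switch on Day 169 and Week 52 on Day 365 (protocol Table 6-1). The switch is first dose + 168 days, and post-switch onsets run from Day 170 to Day 365, which is 196 days.
- Screening of up to 70 days (10 weeks, protocol summary).
- Assumptions: first-dose dates are spread evenly over a 365-day year, onsets are spread evenly over the window concerned, and the screening events considered ended before dosing.

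**Worked cases**

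| First dose | Switch | True event | Recorded start | Imputed start | Result |
|---|---|---|---|---|---|
| 16 Jan 2017 | 3 Jul 2017 | ended 10 Jan 2017 | Jan 2017 | 17 Jan 2017 | after its own end; treatment-emergent |
| 16 Jan 2017 | 3 Jul 2017 | 20 Jul 2017 | Jul 2017 | 1 Jul 2017 | Week 1-24 (wrong) |
| 16 Jan 2017 | 3 Jul 2017 | 20 Oct 2017 | 2017 | 17 Jan 2017 | Week 1-24 (wrong) |
| 17 Oct 2016 | 3 Apr 2017 | Jul 2017 | 2017 | 1 Jan 2017 | Week 1-24 (wrong) |
| 16 Jan 2017 | 3 Jul 2017 | Oct 2017 | Oct 2017 | 1 Oct 2017 | correct period |
| 15 Mar 2017 | 30 Aug 2017 | Feb 2018 | 2018 | 1 Jan 2018 | correct period |

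**Step 1: screening events dated after the first dose**

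*Day missing.* The event is misdated if its onset is in the first-dose month. A first dose on day d of the month leaves d - 1 such days. Over the year the sum is 7 x 465 + 4 x 435 + 378 = 5,373 (months of 31, 30 and 28 days). Share: 5,373 / (365 x 70) = 5,373 / 25,550 = 21.0%.

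*Only the year known.* The event is misdated if its onset is in the first-dose year. The number of such days is the smaller of 70 and the days already elapsed in the year. The sum is (0 + 1 + ... + 69) + 295 x 70 = 2,415 + 20,650 = 23,065. Share: 23,065 / 25,550 = 90.3%.

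SAP 1.1 gives screening as 8 weeks. With 56 days the shares are 5,373 / 20,440 = 26.3% and (1,540 + 309 x 56) / 20,440 = 18,844 / 20,440 = 92.2%.

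**Step 2: post-switch events dated on or before the switch**

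*Day missing.* The event is misdated only if its onset is in the switch month. By the same month count, 5,373 / (365 x 196) = 5,373 / 71,540 = 7.5%. When the switch falls on the 1st, the imputed date equals the switch date. Leaving those 353 cases out gives 5,020 / 71,540 = 7.0%. The other 92.5% or so stay in the right period.

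*Only the year known.* Let k = 0 to 364 be the first-dose day within the year.

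- Switch in the same calendar year (k = 0 to 196): the 196 - k onset days left in that year are misdated. Sum: 196 x 197 / 2 = 19,306. Onsets in the next year are placed correctly.
- Switch in the next calendar year (k = 197 to 364): all 196 onset days are misdated, because 1 January is on or before the switch. Sum: 168 x 196 = 32,928.

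Share: (19,306 + 32,928) / 71,540 = 52,234 / 71,540 = 73.0%.

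**Step 3: the opposite default**

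Suppose every partial date compatible with the switch were moved past it, with no end date to prevent this. True Period 1 onsets (Days 2 to 169, 168 days) would then be misplaced as follows:

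- Day missing: (5,373 + 365) / (365 x 168) = 5,738 / 61,320 = 9.4%.
- Only the year known: (197 x 168 + 168 x 169 / 2) / 61,320 = (33,096 + 14,196) / 61,320 = 77.1%.

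**The case against.** **Programming Specifications.** SAP 2.8.1 says that date-imputation algorithms will be given there. That document is not available and might contain an end-date check. It would then conflict with the statement in SAP 5.1.2 that the first dose is the only comparison, so the two still need aligning.

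**Rarity.** AEs are sought at every visit, start and end dates are recorded, and entries are queried (protocol 7.1, 8.2, 8.3). After Week 24 the scheduled on-site assessments are at Weeks 36 and 52, so gaps are at most 16 weeks. Year-only dates should therefore be unusual. This stands and limits the practical weight of the 73% and 90% figures.

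**Screening events.** Placing uncertain dates after the first dose errs towards counting events, and does so equally in both arms. This also stands: the effect is noise, not bias between arms. It does not justify a start later than the recorded end.

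**Stronger readings that the documents do not support**

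- *Post-switch events are generally moved back.* They are not. A known month other than the switch month gives the right period, and so does a missing month when the AE year begins after the switch.
- *The rule makes secukinumab look safer.* The rule takes no account of arm. After Week 24 everyone receives secukinumab (protocol 3.1), so both arms gain misdated events in the Week 1-24 tables. With similar late event rates, the difference is roughly unchanged and a ratio moves towards 1. Only the attribution to a drug in former placebo patients is one-sided.
- *An event with no year can never be treatment-emergent.* The SAP sets its start to NULL and labels it uncertain, but does not say how it is classified.
- *All ambiguous dates belong after the switch.* Step 3 shows that this misplaces a similar share in the other direction.

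**Conclusion.** The concern holds in limited form. The firm part is that SAP 5.1.2 can produce a start later than the recorded end and so make a resolved pre-dose event treatment-emergent. Under evenly spread dates and a 70-day screening period, this affects about 21% of such events with the day missing and 90% with only the year known.

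The second part is conditional. Post-switch events can be assigned to Week 1-24 in either arm, for about 7% of those with the day missing and 73% of those with only the year known. In former placebo patients this also credits a secukinumab event to placebo.

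These are shares of partially dated events, not of all events. The documents give no count of partial dates, so no effect on the reported AE rates can be stated, and no net bias in favor of secukinumab is shown.

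**What to change.** Amend SAP 5.1.2 and Table 5.1-2 before the Week 24 lock:

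1. An imputed AE start is never later than the recorded AE end date.
2. An event whose recorded end date is before the first dose is not treatment-emergent.
3. A partial date compatible with both sides of the Week 24 switch keeps the primary rule, but is flagged and listed by arm. The Week 1-24 AE summary is repeated with these events assigned to Period 2 as a sensitivity analysis.
4. The Programming Specifications carry the same rules.

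Items 1 and 2 remove the Step 1 misdating (21.0% and 90.3% fall to 0%) wherever an end date is recorded. Item 3 shows how far the controlled safety comparison depends on ambiguous dates without swapping one misplacement for another of similar size. The cost is a few sentences, minor programming, one listing and one additional table.

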**Table 5.1-2: AE date imputation**

	MON	MON < CFM	MON = CFM	MON > CFM
	MISSING			
YYYY MISSING	NULL	NULL	NULL	NULL
	Uncertain	Uncertain	Uncertain	Uncertain
YYYY < CFY	( D ) = 01JULYYYY	( C )= 15MONYYYY	( C )= 15MONYYYY	( C )= 15MONYYYY
	Before Treatment Start	Before Treatment Start	Before Treatment Start	Before Treatment Start
YYYY = CFY	(B)= TRTSTD+1	( C )= 15MONYYYY	(A)= TRTSTD+1	(A)= 01MONYYYY
	Uncertain	Before Treatment Start	Uncertain	After Treatment Start
YYYY > CFY	(E)= 01JANYYYY	(A)= 01MONYYYY	(A)= 01MONYYYY	(A)= 01MONYYYY
	After Treatment Start	After Treatment Start	After Treatment Start	After Treatment Start
Before Treatment Start	Partial indicates date prior to Treatment Start Date			
After Treatment Start	Partial indicates date after Treatment Start Date			
Uncertain	Partial insufficient to determine relationship to Treatment Start Date			
LEGEND:				
(A)	MAX(01MONYYYY,TRTSTD+1)			
(B)	TRTSTD+1			
(C)	15MONYYYY			
(D)	01JULYYYY			
(E)	01JANYYYY			

### 5.1.3 Concomitant medication date imputation

Concomitant medication (CMD) date imputation uses both a comparison of the partial CMD start date to the treatment start date, and the value of the CMDTYP1C flag (1, 2, or 3). Event date comparisons to treatment start date are made based on the year and month values only (any day values are ignored) in Table 1-3 below.

1. If the CMD start date year value is missing, the date will be imputed based on the CMDTYP1C flag value. If the flag value is 1 or 3, the imputed CMD start date is set to one day before the treatment start date. Else, if the flag value is missing or 2, the imputed CMD start date is set to one day after the treatment start date. (Note that for some legacy data, the CMDTYP1C variable may not exist in the data. When this happens and the CMD start date year value is missing, the imputed date value will be NULL.)
2. If the CMD start date year value is less than the treatment start date year value, the CMD started before treatment. Therefore:
  - a. if the CMD year is less than the treatment year and the CMD month is missing, the imputed CMD start date is set to the mid-year point (01JulYYYY).
  - b. Else if the CMD year is less than the treatment year and the CMD month is not missing, the imputed CMD start date is set to the mid-month point (15MONYYYY).

If the CMD start date year value is greater than the treatment start date year value, the CMD started after treatment. Therefore:

- a. If the CMD year is greater than the treatment year and the CMD month is missing, the imputed CMD start date is set to the year start point (01JanYYYY).
- b. Else if the CMD year is greater than the treatment year and the CMD month is not missing, the imputed CMD start date is set to the month start point (01MONYYYY).

- 3. If the CMD start date year value is equal to the treatment start date year value:
- a. and the CMD month is missing or the CMD month is equal to the treatment start month,
  - i. If the flag value is 1 or 3, the imputed CMD start date is set to one day before the treatment start date.
  - ii. Else, if the flag value is missing or 2, the imputed CMD start date is set to one day after the treatment start date.
- b. Else if the CMD month is less than the treatment start month, the imputed CMD start date is set to the mid-month point (15MONYYYY).
- b. Else if the CMD month is greater than the treatment start month, the imputed CMD start date is set to the start month point (01MONYYYY).

**Table 5.1-3: CMD date imputation**

	MON MISSING	MON < CFM	MON = CFM	MON > CFM
YYYY MISSING	(F)	(F)	(F)	(F)
	Uncertain	Uncertain	Uncertain	Uncertain

YYYY < CFY	(D)=01JULYYYY	(C)=15MONYY	(C)=15MONYY	(C)=15MONYY
	Before Treatment Start	Before Treatment Start	Before Treatment Start	Before Treatment Start
YYYY = CFY	(B)	(C)=15MONYY	(B)	(A)=01MONYYYY
	Uncertain	Before Treatment Start	Uncertain	After Treatment Start
YYYY > CFY	(E)= 01JANYYYY	(A)=01MONYYYY	(A)=01MONYYYY	(A)=01MONYYYY
	After Treatment Start	After Treatment Start	After Treatment Start	After Treatment Start
Before Treatment Start	Partial indicates date prior to Treatment Start Date			
After Treatment Start	Partial indicates date after Treatment Start Date			
Uncertain	Partial insufficient to determine relationship to Treatment Start Date			
LEGEND:				
(A)	MAX(01MONYYYY,TRTSTD+1)			
(B)	IF CMDTYP1C IN (1,3) THEN TRTSTD-1 ELSE IF CMDTYP1C in(., 2) THEN TRTSTD+1			
(C)	15MONYYYY			
(D)	01JULYYYY			
(E)	01JANYYYY			
(F)	IF CMDTYP1C IN (1,3) THEN TRTSTD-1 ELSE IF CMDTYP1C in (., 2) THEN TRTSTD+1			

### 5.1.3.1 Prior therapies date imputation

Not applicable

### 5.1.3.2 Post therapies date imputation

Not applicable

### 5.1.3.3 Other imputations

## 5.2 AEs coding/grading

The verbatim term recorded on CRF will be identified as adverse event and will be coded by primary system organ class and preferred term using Medical Dictionary for Regulatory Activities (MedDRA) version 18.1 and above.

## 5.3 Laboratory parameters derivations

Refer to main section to SAP

## 5.4 Statistical models

### 5.4.1 Primary analysis

The primary analysis will be performed comparing treatments with respect to the primary efficacy variable in a logistic regression model with the factors treatment, country and stratification factor diagnosis (PsA or axSpA).

```
Proc logistic data=aaa;  
Class TRT COUNTRY STRATA / param=glm;  
Model AVAL = TRT COUNTRY STRATA;  
Lsmeans TRT / diff cl exp;  
Ods output diffs=lsm_diff;  
Run;
```

In cases where separation is a concern for the primary endpoint at Week 24, e.g. 0% or 100% response in one treatment (sub)group, an exact logistic regression model will be applied to all visits. To ensure convergence, this model will not include any continuous covariates.

SAS Code for Logistic model:

```
Proc logistic data=aaa exactonly;  
Class TRT STRATA / param=glm;  
Model AVAL = TRT STRATA;  
Exact TRT / estimate=both;  
Ods output exactoddsratio=exactoddsratio;  
Run;
```

For subgroup analysis, the above code will be used for each stratification factor.

The primary model will also be recalculated with the above factors included as well as with respective terms for a subgroup\*treatment interaction.

